3. STUDY ESTIMANDS

Hypothetical and treatment policy estimand for primary efficacy endpoint:

Attribute	Details
Treatments	GLPG3970 (400 mg q.d.) vs. Placebo
Population	
• Population target defined through the inclusion/exclusion criteria (see CSP).• Analysis Set: Full Analysis Set (FAS), defined as all randomized subjects

	who have received at least 1 dose of IP.
Endpoint	Change from baseline in DAS28 (CRP) at Week 6.
Population-level summary	Difference (GLPG3970-Placebo) in least square mean (LSM). For further details see study SAP section 6.2.2.2 .
Intercurrent events and strategies to handle those	
• Early treatment discontinuation (for any reason) is handled using the hypothetical strategy• Other intercurrent events (e.g. major protocol violations, intake of prohibited medication, lack of compliance) are handled using the treatment policy strategy (i.e. they are ignored)

Estimand for the secondary objective (safety)

Attribute	Details
Treatments	GLPG3970 (400 mg qd) vs. Placebo
Population	
• Population target defined through the inclusion/exclusion criteria (see CSP).• Analysis Set: Safety Analysis Set, defined as all subjects who were administered IP at least once.
Endpoint	Presence of TEAE
Population-level summary	Percentage of subjects with TEAEs.
Intercurrent events and strategies to handle these	Intercurrent event: early treatment discontinuation (for any reason): handled using the while-on-treatment strategy. It is expected that no further data collection happens after treatment discontinuation, except of course the normal FU visit. All collected data up to (and including) the last contact FU visit is regarded as possibly

	
influenced by the drug exposure and thus will be used in the analysis.
 
Intercurrent event: major protocol deviations, intake of prohibited/rescue medication, lack of compliance: handled using the treatment policy strategy. All collected data will be used in the analysis.

--	---

4. GENERAL METHODOLOGY

4.1. Analysis Sets

The analysis set will always be indicated in a subtitle in the table, listing or figure.

4.1.1. All Screened Analysis Set

All subjects who signed and dated an informed consent form (ICF).

4.1.2. All Randomized Analysis Set

All screened subjects who were randomized into the clinical study.

4.1.3. Safety Analysis Set

All subjects who have been administered at least 1 dose of IP.

4.1.4. Full Analysis Set

All randomized subjects who have been administered at least 1 dose of IP.

4.1.5. Pharmacokinetic Analysis Set

Subset of the Safety Analysis Set for which plasma concentration data are available to facilitate development of the Population PK model as described in the pharmacometric analysis plan and excluding CSP deviations which have an impact on the PK analysis.

For population PK modeling, besides the plasma concentration, the corresponding PK sampling time and the time of last drug intake prior to taking the sample should be available. The results from the population PK analysis will be presented in a separate document.

4.1.6. [REDACTED]

[REDACTED]

4.1.7. [REDACTED]

[REDACTED]

4.2. Randomized Versus Actual Treatment Group

For subject information and efficacy parameters, the treatment group as assigned by the randomization will be used in the analysis (i.e. as-randomized analysis).

The actual treatment groups will be used for the analysis of safety, PK and PD parameters. The “actual” rather than “randomized” treatment will be used only in case the “wrong” drug had been taken during the entire study duration.

Differences between the randomized and actual treatment group will be listed in the disposition/randomization section of the analysis.

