All safety analyses will be performed using the Safety Analysis Set, consisting of all subjects who used at least 1 dose of IP. All safety data collected on or after the first dose of IP administration up to the last contact after the last dose of IP, unless specified otherwise, will be summarized by treatment group according to the IP received. Clinical safety will be addressed by assessing AEs, laboratory assessments, physical examinations, vital signs, and 12-lead electrocardiograms (ECGs).

Efficacy Analysis

All efficacy analyses will be performed using the Full Analysis Set, consisting of all randomized subjects who received/used at least 1 dose of IP. Continuous efficacy endpoints, including the primary endpoint: mixed model for repeated measures to compare treatment groups, with a 90% confidence interval (CI) of the treatment difference at each time point. Binary efficacy endpoints will be presented with a 90% exact CI of the treatment difference at each time point. For the primary efficacy endpoint: go/consider/stop methodology will be used additionally to provide further insight in the treatment effect.

PK Analysis

Descriptive statistics will be done on C_{trough} plasma levels for GLPG3970. Observed plasma C_{trough} for GLPG3970 [REDACTED] will be reported in the clinical study report (CSR).

Observed GLPG3970 plasma concentrations will be analyzed using a population PK approach to characterize the PK profile of GLPG3970. This analysis will provide simulated population pharmacokinetic (pop-PK) parameters for GLPG3970. [REDACTED]

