9.3.5. Analyses of Safety Data

All safety analyses will be performed using the Safety Analysis Set (Section 9.2.4). All safety data collected on or after the first dose of IP administration up to the last contact after the last dose of IP, unless specified otherwise, will be summarized by treatment group according to the IP

received. Clinical safety will be addressed by assessing AEs, laboratory assessments, physical examinations, vital signs, and 12-lead ECGs.

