6.1.9.2. Presentation of Results

Summary statistics per planned treatment group and overall will be provided for each compliance and extent of exposure parameter for IP administration. Frequency tables will be provided for the compliance parameters, using the following categories: <80%; 80% ≤ x < 100%; 100%; 100% < x ≤ 120%; > 120%.

All original IP administration records will be listed per subject. The listing will include all deviations from IP schedules such as missed or reduced doses and GLPG3970/placebo switches and will also include food intake status at the time of IP administration. IP exposure and compliance data will be listed.

For MTX administration, a table summarizing the number and percent of subjects taking MTX by planned treatment group and overall will be provided. In addition, the following parameters will be summarized:

- Dose at baseline (mg);
- Route at baseline;
- Dose form at baseline;
- *Total treatment duration* (days);
- *Total treatment duration, excluding days off MTX*

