6.7. Changes to the Planned Analyses, Not Covered by Protocol Amendments

Not applicable.

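### SAP 4.2 tabulates a placebo subject who took GLPG3970 for part of the study as placebo, narrowing the protocol's as-received safety rule without declaring it

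*SAP*

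**What the plan says.** The protocol states the grouping rule for safety in its synopsis and again in section 9.3.5: safety data "will be summarized by treatment group according to the IP received". Neither place sets a minimum duration, and neither says what to do with a subject who received both products.

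SAP 4.2 starts in the same way: "The actual treatment groups will be used for the analysis of safety, PK and PD parameters". Its next sentence restricts this. Actual treatment replaces randomised treatment only if the wrong "drug had been taken during the entire study duration". The Safety Analysis Set in SAP 4.1.3 ("All subjects who have been administered at least 1 dose of IP") settles who is included, not in which arm.

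SAP 6.1.9.2 anticipates mixed exposure. It says of the IP administration records: "The listing will include all deviations from IP schedules such as missed or reduced doses and GLPG3970/placebo switches". SAP 4.2 and 6.1.2 add listings of differences between assigned and actual treatment. No safety table is adjusted.

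Protocol section 9 requires departures from the protocol to be justified in the SAP. SAP 6.7, the section for changes to the planned analyses, reads "Not applicable".

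**The concern.** Safety and tolerability against placebo is a secondary objective, and the safety estimand in SAP section 3 is the percentage of subjects with TEAEs. If a placebo subject takes GLPG3970 for some weeks and an adverse event, laboratory shift or ECG change starts in that time, SAP 4.2 counts it as placebo. The placebo rate goes up, the GLPG3970 rate does not, and the apparent excess on GLPG3970 shrinks.

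This sits oddly with the SAP's other safety conventions, which resolve doubt towards the drug. Missing relatedness counts as IP-related (6.3.1.4), and an event that could belong to either period is placed in the treatment period (6.3.1.3).

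The case is possible in practice. The schedule of activities has IP dispensed at Visits 1, 3 and 4 (Days 1, 15 and 29), and protocol 7.3 allows several kits per visit. An error can therefore affect part of the six weeks and not the rest.

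**Working it through.** No figure in the documents depends on this rule, so there is none to reproduce. The check has two parts.

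**1. What each text does with each kind of subject**

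| Randomised to | Took | SAP 4.2 | Any-dose rule (proposed for safety) |
|---|---|---|---|
| Placebo | GLPG3970 throughout | GLPG3970 | GLPG3970 |
| Placebo | Both products | Placebo | GLPG3970 |
| Placebo | Only GLPG3970, stopped early | Unclear | GLPG3970 |
| GLPG3970 | Both products | GLPG3970 | GLPG3970 |
| GLPG3970 | Placebo throughout | Placebo | Placebo |

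The protocol's wording, by product received, settles the first and last rows. For a subject who took both products it does not name an arm, but an arm that ignores the GLPG3970 intake does not fit the wording. In the third row, SAP 4.2 turns on whether the whole-study condition means all the dosing that took place or the full six weeks.

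**2. Scale**

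Inputs from the documents: 15 subjects planned on GLPG3970 and 10 on placebo (protocol 5.1, SAP 2.3). Assumption: one placebo subject takes GLPG3970 for part of the study. All event counts below are also assumed.

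Let *g* and *p* be the numbers of other subjects with a TEAE in the GLPG3970 and placebo arms. Let *e* = 1 if the switched subject has a TEAE and 0 if not.

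- SAP rule: difference = g/15 − (p + e)/10
- Any-dose rule: difference = (g + e)/16 − p/9

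One subject is 1/10 = 10 points of placebo incidence, and 1/15 = 6.7 or 1/16 = 6.25 points of GLPG3970 incidence.

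| Case | g, p, e | SAP rule: GLPG3970 vs placebo | Difference | Any-dose rule: GLPG3970 vs placebo | Difference | Shift |
|---|---|---|---|---|---|---|
| A | 0, 0, 1 | 0/15 = 0% vs 1/10 = 10% | −10.0 | 1/16 = 6.25% vs 0/9 = 0% | +6.25 | +16.25 |
| B | 3, 0, 1 | 3/15 = 20% vs 1/10 = 10% | +10.0 | 4/16 = 25% vs 0/9 = 0% | +25.0 | +15.0 |
| C | 5, 2, 1 | 5/15 = 33.3% vs 3/10 = 30% | +3.3 | 6/16 = 37.5% vs 2/9 = 22.2% | +15.3 | +11.9 |
| D | 3, 0, 0 | 3/15 = 20% vs 0/10 = 0% | +20.0 | 3/16 = 18.75% vs 0/9 = 0% | +18.75 | −1.25 |
| E | 5, 2, 0 | 5/15 = 33.3% vs 2/10 = 20% | +13.3 | 5/16 = 31.25% vs 2/9 = 22.2% | +9.0 | −4.3 |

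In cases A to C the switched subject has an event, and the rule moves the difference by about 12 to 16 points. In case A it reverses the sign. In cases D and E the subject has no event. The shift is small and runs the other way, because the any-dose rule adds an event-free subject to the GLPG3970 denominator.

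Timing matters as well. If the event in cases A to C began on placebo before the switch, the SAP rule attributes it correctly and the any-dose rule does not.

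**The case against.** **The protocol leaves a gap, and the SAP may only be filling it.** This stands in part. The protocol has no explicit rule for a subject who received both products. A reader might infer that SAP 4.2 breaks an express rule and that the entry in 6.7 is false. The documents do not support that much. They do show a narrowing of the protocol's plain wording, and of the SAP's own preceding sentence, with no justification given. The any-dose rule is not protocol text either; it is one way of honouring that wording.

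**The present rule need not favour the drug.** This stands. A reader might infer that it always understates the GLPG3970 risk. That fails if the switched subject has no event (cases D and E), and it fails as to attribution if the event came before the switch.

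**Correction does not require three wrong dispensings.** This stands. A reader might infer that it does, since IP is dispensed three times. A subject given only the wrong product who stops before the next dispensing could arguably be reclassified after a single error. The text leaves this open.

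**A switch may never happen, and it would be visible.** The first half stands: allocation is central, kits carry unique numbers and accountability is checked (protocol 6.5.1, 7.3 and 7.5). On visibility, SAP 6.1.9.2 lists "missed or reduced doses and GLPG3970/placebo switches", 6.3.1.6 lists the relative start day of each event, and SAP 6.3 plans no formal safety testing. In a trial of 25 subjects a careful reader could trace the case. The listings would still leave the tables uncorrected, and the tables carry the group comparison.

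**The estimand already covers this.** SAP section 3 handles major deviations and poor compliance by treatment policy. That strategy keeps the subject's data in the analysis. It does not say in which arm they are counted when SAP 4.2 itself calls for actual treatment.

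**Conclusion.** The concern holds as a bounded one. SAP 4.2 narrows the protocol's as-received grouping for safety, does not declare it in 6.7, and leaves a part-exposed placebo subject in the placebo tables, so events that began on GLPG3970 would count against the comparator.

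The effect is conditional on a switch. Given one, a single subject is 10 points of placebo incidence, and under the assumed counts the choice of rule moves the difference by about 12 to 16 points upward if that subject has an event, or about 1 to 4 points downward if not. These are illustrations, not forecasts, and they rest on the planned 15 and 10 subjects. The primary efficacy analysis is untouched, because efficacy is analysed as randomised. The change is worth making because it is cheap and easily settled before unblinding.

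**What to change.** Before unblinding:

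1. In SAP 4.2, limit the existing whole-study sentence to PK and PD. It should not simply be deleted, because it is the SAP's only statement of when actual treatment applies to those parameters.
2. Add for safety: *A subject who received at least one dose of GLPG3970 is analysed in the GLPG3970 group; a subject who received only placebo is analysed in the placebo group.*
3. For any switched subject, flag each TEAE in the listings by whether it began before or after the first GLPG3970 dose.
4. Record the rule in SAP 6.7, as protocol section 9 requires of departures from the protocol.

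The cost is a short edit to 4.2, an entry in 6.7, one derived treatment variable for safety and one listing flag. The downside is that a switched subject's placebo-period events and event-free time both count under GLPG3970, even after a single mistaken dose. The flag shows the events; it does not show the event-free time.

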4.3. Analysis Periods and Analysis Time Points

4.3.1. Relative Day

The timing of an assessment or an event relative to a reference date will be calculated as follows:

When the concerned date is before the reference date:

$$\text{Relative day (days)} = \text{concerned date} - \text{reference date}$$

When the concerned date is the equal to or later than the reference date:

$$\text{Relative day (days)} = \text{concerned date} - \text{reference date} + 1 \text{ day}$$

where:

- The *concerned date* could be the measurement date of the assessment, or the start or end date of the event.
- The *reference date* default is the date of the first dose of IP administration, unless specified otherwise.
- *Date* implies a complete date having day, month and year available. Unless otherwise specified, the *relative day* will remain missing when it cannot be calculated due to absence or incompleteness of the concerned and/or reference dates.

The general terms of this formula also apply when similar relative timings are required in other time units, for example in minutes.

4.3.2. Analysis Periods

For treated subjects, adverse events and assessments will be allocated to analysis periods according to

Table 1.

Table 1 Analysis Periods

Analysis Period	Start Analysis Period	End Analysis Period
Screening	Date of signing the ICF, with 00:00 added as time part	Date (time) of first IP administration - 1 minute
Treatment	Date (time) of first IP administration.	Study termination date (i.e. date of last contact), with 23:59 added as time part

The last analysis period will always end on the date of last contact.

For every subject, all assessments performed and all events occurring during the study are expected to have a (start) date (/time) between the date of informed consent (IC) signature and the last contact date. Obvious exemptions are historical records like medical history or concomitant therapies having started before the study.

Assessments and events will be allocated to one of these analysis periods by incidence, meaning placing the record (start) date and time between the matching start and end dates and times of the subject's own analysis periods, assuming completeness of all dates and times, or further determined by the presence of timing indicators such as tick boxes flagging AEs starting before/after first IP administration, or by worst-case considerations for AEs if needed. For the parameters for which the time of assessment was not planned to be collected, their assessment on the day of first IP administration will be considered as baseline and will be reported under the 'Screening' analysis period with the exception of AEs.

4.3.3. Analysis Windows

For the efficacy, PK, [REDACTED] and safety assessments, all data (including data obtained at unscheduled visits) will be placed into time windows based on the relative day (ADY) of the assessment (relative to the first dose of IP), according to the following allocation tables:

For endpoints with multiple components, analysis windows will be derived separately for each component/parameter.

Table 2: Analysis Visit Window for non-PK data

Visit date and time	Relative day (ADY)	Assessment visit (VISIT)	Time window (in ADY)	Target day	Analysis visit (AVISIT)
On or before first study drug administration	≤ 1	Last assessment at any point in time before first study drug administration	≤ 1	1	Baseline
After first study drug administration	>1	Any scheduled (non follow-up), unscheduled, or early discontinuation visit	2 to 12	8	Week 1
			13 to 22	15	Week 2
			23 to 36	29	Week 4
			37 to 49	43	Week 6
		Follow-up	CRF collected follow-up visit		Follow-up

Table 3: Analysis Visit Window for PK data

Visit date and time	Relative day (ADY)	Assessment visit (VISIT)	Time window (in ADY)	Target day	Analysis visit (AVISIT)	Analysis time point (ATPT)
Before first study drug administration	<1 or pre-dose at ADY=1	Last assessment at any point in time before first study drug administration	<1 or pre-dose at ADY=1	1	Baseline	Pre-dose (within 30 minutes prior to dosing)
Same as or after first study drug administration	≥ 1	Any scheduled (non follow-up), unscheduled, or early discontinuation visit	1	1	Day 1	As indicated in the database: 0.5-1.5, 2-2.5 hours post-dose
			13 to 22	15	Week 2	As indicated in the database: Pre-dose (within 30 minutes prior to dosing)
			23 to 36	29	Week 4	As indicated in the database: Pre-dose (within 30 minutes prior to dosing)
			37 to 49	43	Week 6	As indicated in the database: Pre-dose (within 30 minutes prior to dosing) and within [4-6 hours post dose].

Visit date and time	Relative day (ADY)	Assessment visit (VISIT)	Time window (in ADY)	Target day	Analysis visit (AVISIT)	Analysis time point (ATPT)
		Follow-up	CRF collected follow-up visit		Follow-up	

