8.2. Unscheduled Visits

Additional visits can be performed at other time points for any safety assessments, if clinically indicated. These unscheduled visits and outcomes of additional assessments need to be recorded in the source and, if performed before the subject's last visit per CSP, also in the CRF.

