4.3.5. Selection and Use of Analysis Visits

Before first administration of IP, only Baseline will be used for the entire statistical analysis. Pre-baseline assessments will only be listed. After first administration of IP, if multiple valid, non-missing assessments exist in an analysis window, records will be chosen based on the following rules if a single value is needed:

- The record closest to the nominal day for that visit will be selected, or
- If there are 2 records that are equidistant from the nominal day, or more than 1 record (with time known) on the selected day, the latest record will be taken
- If chronological order cannot be determined (e.g., more than 1 record on the same day with time missing), the average of the records will be computed and reported in the analysisFor the composite endpoints including DAS28 (CRP), [REDACTED], the following steps will be used to derive [REDACTED], unless otherwise specified:
- Step 1: Put [REDACTED] component value into an analysis visit window.

- Step 2: Within each visit window, select the data points for analysis.
- Step 3: Combine these selected data points within each analysis visit window across the components

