6.2.2.1. Derivation Rules

The DAS assessment is a derived measurement with differential weighting given to each component. The DAS28 (CRP) will be calculated at each assessment time point.

The components of the DAS28 arthritis assessment include:

- Tender Joint Count 28 (TJC28) ranges from 0-28
- Swollen Joint Count 28 (SJC28) ranges from 0-28
- High sensitivity C-reactive protein (hsCRP) (in mg/L)
- Patient's disease activity VAS (in mm) (ranges from 0 = best to 100 = worst)

The DAS28 (CRP) score will be calculated using the below formula:

$$\text{DAS28 (CRP)} = 0.56 \times \sqrt{\text{TJC28}} + 0.28 \times \sqrt{\text{SJC28}} + 0.36 \times \text{Ln}[1+\text{CRP}(\text{in mg/L})] + 0.014 \times \text{patient's disease activity VAS} (\text{in mm}) + 0.96 \text{ (Mack, Hsia, \& Aletaha, 2017)}$$

where Ln is the natural logarithm

A lower score is considered as better disease activity. If one of the component is missing at a specific analysis visit, DAS28 (CRP) will not be calculated for that assessment and will be set to missing.

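### DAS28 (CRP) is built from components selected one by one, so an unscheduled hsCRP can occasionally replace the one taken with the Week 6 joint counts and VAS

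*SAP*

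**What the plan says.** SAP 4.3.3 (Analysis Windows) applies to efficacy and safety data alike: "all data (including data obtained at unscheduled visits) will be placed into time windows based on the relative day (ADY) of the assessment". The Week 6 window is relative days 37 to 49 with target day 43; the Week 4 window is days 23 to 36 with target day 29. For composites it adds: "For endpoints with multiple components, analysis windows will be derived separately for each component/parameter".

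SAP 4.3.5 (Selection and Use of Analysis Visits) then chooses one record per window: "The record closest to the nominal day for that visit will be selected". Where records are equally distant, or several timed records fall on the chosen day, the latest is used. DAS28 (CRP) is named as a composite handled in this order: window the component values, select within the window, and finally "Step 3: Combine these selected data points within each analysis visit window across the components".

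The only further condition is in SAP 6.2.2.1: "If one of the component is missing at a specific analysis visit, DAS28 (CRP) will not be calculated for that assessment". It deals with missing components and is silent on their dates.

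On the protocol side, hsCRP belongs to the clinical chemistry safety panel (8.5.2), and section 8.2 allows unscheduled visits: "Additional visits can be performed at other time points for any safety assessments, if clinically indicated". Section 8.1 and footnote 1 of the Schedule of Activities plan questionnaires, joint counts and blood sampling as one sequence on the visit day, within 3 hours before dosing unless otherwise specified.

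**The concern.** The protocol plans the DAS28 components as one set, taken at one visit and before that day's dose. The SAP does not keep the set together. Joint counts and patient VAS will normally exist only at scheduled or early discontinuation visits. hsCRP can also be measured at an unscheduled safety visit, so it is the component most likely to come from another day.

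Unscheduled visits are made when clinically indicated. An hsCRP drawn then may reflect an intercurrent illness more than RA activity. IP is taken on site at Visit 5 and none is dispensed there, so a draw after an early Visit 5 also comes after the last dose. The primary Week 6 score could then combine measurements from different days although a complete same-day set was available. What is at stake is avoidable noise in a primary endpoint measured on 15 and 10 subjects, with some directional error if such draws are more common in one arm.

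**Working it through.** **1. When can the visit's hsCRP be displaced?** The rule (closest to Day 43, latest on ties) was applied to a Visit 5 hsCRP and one unscheduled hsCRP on another day of the Week 6 window.

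| Visit 5 on day | Displaced by an unscheduled hsCRP on day |
|---|---|
| 41 | 42, 43, 44, 45 |
| 42 | 43, 44 |
| 43 | none |
| 44 | 43 |
| 45 | 42, 43, 44 |

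On any of these days a later timed draw on the same day also displaces the earlier one. Inside the ±2-day visit window the largest gap between joint counts and hsCRP is 45 − 41 = 4 days. In that case the hsCRP is also 4 days after the last dose, which was taken at the Day 41 visit. If the visit itself falls outside ±2 days, the gap can reach 49 − 37 = 12 days, because Days 37 and 49 are equally far from 43 and the later is taken.

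**2. Effect on one subject.** SAP 6.2.2.1 gives the CRP term as 0.36 × ln(1 + CRP in mg/L), so replacing CRP₁ by CRP₂ changes DAS28 by 0.36 × ln[(1 + CRP₂)/(1 + CRP₁)]. The documents give no CRP distribution, so the values below are assumptions. The SD of 1.3 is from the sample size section (protocol 9.1, SAP 2.6).

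| CRP₁ to CRP₂ (mg/L) | Calculation | Shift | Shift / 1.3 |
|---|---|---|---|
| 8 to 20 | 0.36 × ln(21/9) | +0.31 | 0.23 |
| 8 to 40 | 0.36 × ln(41/9) | +0.55 | 0.42 |
| 8 to 80 | 0.36 × ln(81/9) | +0.79 | 0.61 |

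The shift can also be downward: 20 replaced by 5 gives −0.45.

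**3. Effect on the treatment comparison.** The standard error of the difference is 1.3 × √(1/15 + 1/10) = 0.531. To check this yardstick, the plan's own operating characteristics were reproduced with a flat-prior normal posterior. A signal requires the estimate to be below −0.6 − 0.8416 × 0.531 = −1.047 (the P80 condition, which is stricter than the P10 cut-off of −1.6 + 1.2816 × 0.531 = −0.920).

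| True difference | Plan: signal / no conclusion / no signal | Reproduced |
|---|---|---|
| −1.6 | 0.852 / 0.043 / 0.105 | 0.851 / 0.049 / 0.100 |
| −0.6 | 0.192 / 0.091 / 0.717 | 0.200 / 0.073 / 0.727 |

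All six agree within 2 percentage points.

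One subject at +0.546 moves the arm mean by 0.546/15 = 0.036 on GLPG3970 or 0.546/10 = 0.055 on placebo. Relative to 0.531 these are 0.07 and 0.10 standard errors.

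The probability of a signal at the target value was also checked with GLPG3970 subjects affected, assuming CRP of 10 replaced by 20 (+0.233) or by 50 (+0.552):

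| Affected on GLPG3970 | 10 to 20 | 10 to 50 |
|---|---|---|
| 0 | 0.851 | 0.851 |
| 1 | 0.845 | 0.835 |
| 3 | 0.830 | 0.798 |

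**The case against.** The strongest reply is that the trigger is narrow. Visit 5 must miss Day 43 or be followed by a later same-day draw. An unscheduled draw must then be closer to Day 43, or tied and later, and it must include hsCRP. A Day 43 visit cannot be displaced by another day's sample. Follow-up visits are kept out of the Week 6 window, and an early discontinuation visit repeats all Visit 5 assessments, so it normally supplies a full set. This stands: the event is probably uncommon.

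The separate-component rule also has a purpose. DAS28 is missing if any component is missing, and the protocol foresees home, local and remote visits during the pandemic, so components may be collected on different dates. This stands too, and the fix has to keep that benefit.

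SAP 4.3.5 applies unless otherwise specified, and SAP section 1 places technical derivation details in a separate document. A same-visit priority might be written there. It cannot be seen, and nothing in SAP 6.2.2 supplies one.

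Four stronger readings are tempting but not supported:

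- **Unscheduled draws usually include hsCRP.** No section says that an unscheduled draw runs the full panel. The one repeat-testing list spelled out, for liver monitoring in protocol Appendix 8, omits CRP. Section 8.1.1 allows one resample of safety tests for technical or transport reasons only, so not every repeat is prompted by illness.
- **Off-treatment CRP enters at Week 4 as well.** Dosing is daily through that window, so this does not generally apply. Week 4 enters the primary analysis only as another repeated measure in the MMRM.
- **A shift of 0.55 nearly equals the lower reference value of 0.6.** That value is a difference between group means. The yardstick for one subject is the SD of 1.3.
- **The rule could manufacture a signal for the drug.** Protocol 5.5 names a possible rise in infection risk on GLPG3970 but forecasts no imbalance. If infections did raise CRP more often in that arm, DAS28 would rise there and the error would work against the drug. Under the treatment policy strategy in SAP section 3, illness-raised CRP at a scheduled visit may count anyway, and the fix would not remove it.

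**Conclusion.** The gap is real and follows from the SAP text: components are selected one by one, unscheduled data are eligible, and nothing ties the hsCRP to the visit that supplied the joint counts and VAS. It is a cheap improvement and does not threaten the primary conclusion. An affected subject's score could move by about 0.2 to 0.6 SD, but one subject at +0.55 moves an arm mean by only 0.04 to 0.05, about 0.1 SE or less. If an infection prompts the draw, the substitution adds noise and tends to work against the arm with more such draws.

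The sizes rest on assumed CRP values, the planned 15 + 10 subjects and the assumed SD of 1.3. The frequency cannot be derived from the documents. The conclusion also assumes that the separate derivation document contains no same-visit rule.

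**What to change.** In SAP 4.3.5, for DAS28 (CRP) and other composites:

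1. Within each window, select the date closest to the nominal day on which both joint counts and patient VAS were done.
2. Use the hsCRP from that same visit.
3. Only if that value is missing, use another hsCRP in the window, choosing the one nearest to the joint-count date.

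Limit the sentence on separate component windows in SAP 4.3.3 accordingly. Step 3 keeps the data-saving benefit of the present rule when a visit is incomplete. The wording should be settled before unblinding.

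The cost is SAP text and derivation code, with no new data and no change in sample size. The one downside is that the hsCRP used in DAS28 may differ from the value in the stand-alone hsCRP table for the same window; a table footnote would cover this.
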